3.3 Other Outcome Measures

- 1) ART or RIF exposure in plasma: Targeted concentrations of ART/TB medications (Note: according to single sample testing, no PK parameters will be modeled):
 - EFV : concentration from sample drawn 12-20 hours post previous dose EFV
 - DTG: concentration from sample drawn 20-28 hours post previous dose DTG
 - RIF: concentration from sample drawn 1-16 hours post previous dose RIF

The actual time/concentration profile will be plotted for each target drug (and indicating study group for EFV). Summary statistics for the distribution of targeted drug concentrations will be provided.

For each drug/metabolite, concentrations will be categorized into 2 groups based on adequate exposure versus inadequate exposure as follows:

EFV: threshold of 650 ng/mL (reference: lower 95% prediction bound on EFV concentration 20 hours post-dose from population PK modeling as published in Csajka et.al. Clinical Pharmacology and Therapeutics, 73:1, 2003)
DTG: threshold of 398 ng/mL (based on lower 95% bound of Ctrough of 50mg dose)
RIF (and associated metabolite desacetyl RIF): LLOQ of the assay (i.e. 75 ng/mL for RIF, 37.5 ng/mL for desacetyl RIF)

Those with documented inadequate exposure to the perpetrator drug, using the thresholds above, will be flagged for exclusion from a secondary, per-protocol analysis of LNG. Note: For RIF, both RIF and desacetyl RIF metabolite need to be LLOQ in order to be excluded in the per-protocol analysis. See below for details.

Note: References for DTG thresholds below:

4 Statistical Principles

4.1 General Considerations

4.1.1 Analysis sets

Full analysis set:

Participants who take LNG study treatment will be included in descriptive analyses of baseline, study conduct and descriptive summaries of AEs and other safety data (see below for separate analysis set for safety outcome measures).

Primary PK analysis set (primary outcome/objective):

Participants must meet all the following:

- Took assigned dose of LNG study medication
- Reported taking scheduled doses of other Rx (ART or TB Rx) over the 72 hours prior to PK sampling and over the 8-hour PK sampling period, as applicable
- Have a AUC(0-8hr) PK parameter estimated

Note: Baseline tables may be repeated for the PK analysis set if this analysis set differs from the Full analysis set.

Per-protocol PK analysis set:

Excluding participants whose perpetrator drug (i.e. EFV, DTG, or RIF) measured concentration was below the pre-specified threshold defined above in section 3.3 above.

Safety analysis set for comparisons of safety outcome measures between single-dose and double-dose LNG:

Participants who receive a dose of LNG that does not match their assigned dose will be excluded from comparisons of single versus double-dose LNG.

4.1.2 Other general considerations

- Because comparisons are not between groups assigned by randomization (except A and B below), there will be exploration of imbalances at baseline between pairs of relevant comparison groups not based upon randomization.

Pairwise comparisons include groups:

- B vs C (related to comparison in primary objective #1)
- D vs C (related to comparison in primary objective #2)
- B vs A (related to comparison in secondary objective #1; randomized)
- A vs C (related to comparison in secondary objective #2)

The baseline characteristics examined will be limited to the following: age (in years), BMI (CDC categories), body fat percentage (categories or continuous), country, race/ethnicity;

and among the HIV study groups: CD4 cell count, detectable plasma HIV-1 RNA, NRTI backbone containing tenofovir. Statistical tests used will be Fisher's exact test (or extension) for dichotomous (other categorical) characteristics, and exact Wilcoxon Rank Sum test for continuous characteristics. Due to the modest sample size, any adjusted analyses may need to adjust one covariate at a time.

Note: other baseline characteristics (e.g. OB/GYN characteristics) may be summarized overall and within study group.

- There will not be any adjustments for multiple testing of safety outcomes due to interim reviews. There will not be significance level adjustment affecting confidence interval calculation for the primary outcome GMRs, as each of the primary pairwise comparisons expressed as a GMR is addressing a separate study objective.

4.2 Analysis Approaches

4.2.1 Calculating Geometric Means, GMRs and associated confidence intervals

The natural (base e) log of concentration based PK parameters will be calculated, and confidence intervals computed based on normality assumptions of the log-transformed data. The respective geometric means and CIs will be calculated by taking the antilog of (exponentiating) both the estimated means and confidence interval bounds. Differences between parallel comparison groups will be calculated as the difference of the log-transformed PK parameters (equivalent to the log of the ratio).

Variance of the difference will assume equal group variances (and thus used pooled variance). Sensitivity analyses will check this assumption by repeating CI estimation using Satterthwaite version of standard error, which does not assume equal variance between groups.

The final GMR and respective CI presented will be the exponentiated point estimate of both the difference, and the confidence bounds on the confidence interval calculated using normality assumptions.

Further details provided in the Analysis Implementation Plan.

4.2.2 Primary PK analysis

In addition to the primary PK analyses described above (calculation of GMR and associated 90% CI on LNG PK parameters), the following supplementary analyses will be conducted to test the robustness of results from this primary analysis (based on the primary PK analysis set):

- 1) Parallel analysis of the per-protocol PK set which excludes participants whose measured perpetrator drug concentration was below the pre-defined threshold.
- 2) Estimation of GMR between non-randomized groups, adjusted for prognostic factors, which may be imbalanced between groups. (Note: adjustment will be performed via normal linear regression modeling on log-transformed PK parameters). (Adjusted

GMRs may also be given for the randomized group comparison so that results presented are parallel and this may be interpreted as adjustment for chance imbalance within a small sample size despite randomization.)

Secondary Objective #3: The outcome to address this objective is AUC_{0-24hr}, and the external comparison groups are the LNG groups as published in Pariditpan Contraception, 2017 (Pharmacokinetics of levonorgestrel and ulipristal acetate emergency contraception in women with normal and obese body mass index), and as results available via clinicaltrials.gov NCT:02689804. Within subgroups defined by normal BMI and obese BMI, the GMR and associated 90% CI for AUC_{0-24hrs} for LNG will be estimated between A5375 Group C (DTG) and this external historical control group. (This analysis will use Satterthwaite calculation of standard error.)

Secondary Objective #5: The outcomes to address this objective including the primary outcome (LNG AUC₀₋₈ hours), as well as the following: C_{max}, and AUC₄₈, C₄₈ (or AUC₂₄ and C₂₄, if too many participants are missing PK parameters at 48 hour). The independent variables include the baseline measurements of body weight including body fat percentage, total weight in kg, and BMI in kg/m². To evaluate the association between these baseline independent variables and the outcome of log-transformed LNG PK parameters, generalized linear regression models will be fit, with additional explanatory variable of LNG dose and perpetrator drug. Geographic region and age will be included for in these models to provide calculation of adjusted GMRs where possible.

5 Report Contents

1. *CONSORT Diagram*
 - a. *Screening and screen failures*
 - b. *Enrollment and eligibility violations*
 - c. *Randomization and Assignment to study groups*
 - d. *Analysis sets and analysis exclusions*
2. *Baseline characteristics*
 - a. *Baseline Characteristics for Full Analysis set*
 - b. *Baseline Characteristics for Primary PK Analysis set*
3. *Targeted medications*
 - a. *Women living with HIV: background ARV regimens*
 - b. *Women with TB: TB medications*
4. *Contraceptive use*
 - a. *Recent contraceptive medications and methods*
5. *Targeted Historical Medical Diagnoses*
6. *LNG Treatment dose received*
7. *Adverse events*
8. *Tolerability of LNG – targeted symptoms before and after LNG receipt*
9. *Analysis of primary outcome measures*
10. *Analysis of secondary outcome measures*
11. *Correlation of baseline body measurements with LNG exposure as measured by AUC_{0-8hr}*

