The effect of food on LNG absorption has not been evaluated. LNG is 97.5-99% protein-bound to sex hormone-binding globulin and albumin, only 2% of LNG is present as unbound drug. This, in addition to an inverse association between LNG concentrations and body weight [27-29], contributes to the high interpatient variability in drug levels. LNG is extensively metabolized to inactive metabolites via the cytochrome P450 (CYP) enzyme system, specifically the CYP3A4 isoenzyme, and co-administration of medications that induce or inhibit CYP3A4 are known to impact LNG concentrations. Approximately 45% of LNG and its metabolites are excreted in the urine and 32% in the feces, and the elimination half-life following a single oral dose LNG is approximately 17 to 24 hours. LNG is not known to influence exposure to ART or TB therapy [21].

LNG PKs are influenced by body weight as measured by BMI. Two studies have evaluated the effect of an overweight or obese BMI on LNG PKs. Edelman et al. found 49% lower  $AUC_{0-2.5h}$  in women with BMI >35 compared to BMI <25 [30]. Pradipan et al. found 52% lower  $AUC_{0-24h}$  in women with BMI >30 kg/m^2 compared to BMI <25 kg/m^2 [31].

Studies have not been conducted to determine the PK parameter that is associated with LNG EC effectiveness. Variable doses of LNG EC have been evaluated, ranging from 0.4 to 1.5 mg, and the studies conducted were not designed to be dose-finding. Therefore, the concentration-response relationship is unknown [32]. Although there is a proposed threshold for LNG implant effectiveness, the mechanism of contraception is not the same between a long-acting contraceptive and EC so this concentration cannot be extrapolated to EC.

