### 10.3 Randomization and Stratification

Enrollment to the study is deterministic (not-randomized) for participants who are currently taking either DTG based ART regimens, or RIF-containing anti-TB regimens; these women are directly assigned to Groups C and D, respectively. Participants on EFV-containing ART regimens will be randomized between Groups A (1.5 mg LNG) and B (3.0 mg LNG) in a 1:2 ratio using permuted block randomization that is dynamically balanced within each **institution**. To guard against potential confounding due to body weight or BMI of the participant, enrollment will be **limited** by BMI in the following manner. Women with BMI  $\geq 30$  kg/m^2 will be limited to no more than five within Groups B-D and no more than three within Group A. Therefore, the overall representation of obese women in the study sample will be limited to no more than 15%. The results of either randomization or enrollment to treatment group will be unblinded to participants, and clinical research site staff.

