85%	74%	97%	86%	(61%, 119%)

Summary of Table 10.4-3. Under modest departures from equivalence, the 90% CI about estimated GMRs observed to be 85% or closer to equivalence (100%) are expected to be bounded above the BE LCB of 70%.

The effective sample size for randomized Group A (15) is based on the secondary objective for a superiority hypothesis (rather than equivalence testing as in the primary study objectives), comparing the randomized Groups A and B (n=30). Here, the ratio is B/A so that the anticipated raw scale ratios are >100 and the significance level has been adjusted to 0.05 so that a 2-sided 95% CI is calculated and compared to see if the confidence interval excludes 100. There is at least 80% power to conclude a difference between the randomized groups for LNG AUC when the true difference between groups is that the increased dose has at least 47% larger AUC of LNG than the standard-dose (or estimated ratio 147.5). A 95% CI for this estimated ratio would be (112, 194).

A participant is considered to be evaluable for the primary objective if the participant completes the 8 hour PK sampling after LNG EC administration. The participant replacement criteria are described in [section 9.0](#). Participants who are not evaluable for the primary outcome for any reason during the period of study accrual will be replaced.

Considering the sample size calculations above, and to protect against 10% loss of the primary outcomes after study accrual is closed, (e.g., problems related to laboratory analysis), the adjusted sample size for this four-group study is 116 female participants—33 each in Groups B-D, and 17 in Group A. (In another ACTG contraception study, A5093, the loss of the primary outcomes of week 12 was 9.8% [6 of 61 participants] due to either sample specimen loss or assay results not available.)

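### The randomised B vs A contrast is estimated with no baseline covariate, and body-size adjustment is optional and unspecified, which may cost precision in a secondary estimate

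*SAP*

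**What the plan says.** **Estimator.** SAP 4.2.1 defines the GMR in the same way for every pair: "Differences between parallel comparison groups will be calculated as the difference of the log-transformed PK parameters (equivalent to the log of the ratio"), with a pooled variance and no covariate.

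**Adjustment.** SAP 4.2.2, item 2, plans covariate-adjusted GMRs as a supplementary analysis of the non-randomised pairs. For the randomised pair, adjusted "GMRs may also be given for the randomized group comparison so that results presented are parallel", or to cover chance imbalance. Precision is not given as a reason, and no covariate is named. SAP 4.1.2 lists the baseline characteristics to be examined for imbalance, including "BMI (CDC categories), body fat percentage (categories or continuous"), and warns that adjusted analyses may have to take one covariate at a time.

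**Test.** In the SAP 3.1 table, superiority of B over A is tested by an exact Wilcoxon rank sum test. The 90% interval for the GMR is a secondary evaluation.

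**Design.** Protocol 10.4: "The effective sample size for randomized Group A (15) is based on the secondary objective for a superiority hypothesis". It adds: "There is at least 80% power to conclude a difference between the randomized groups for LNG AUC" at a ratio of 147.5, with a 95% CI of (112, 194). Protocol 10.6.3 treats covariates for this contrast only as a confounding matter that randomisation removes.

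**Prognostic factor.** Protocol 2.1.1 states that "an inverse association between LNG concentrations and body weight [27-29], contributes to the high interpatient variability in drug levels". It cites AUC reductions of 49% and 52% in obese women. Protocol 3.0 gives the inverse relation with weight and BMI as the reason for the obesity caps.

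**The concern.** Chance imbalance is not the main reason to adjust a randomised comparison. A baseline covariate that predicts the outcome takes variance out of the error term, whether or not the groups happen to differ on it. Here the protocol itself names such a covariate. Height is measured at screening, weight at screening and entry, and BMI is calculated for everyone (Protocol 6.1 and 6.3.5).

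B vs A tells the reader whether doubling the dose raises LNG exposure under efavirenz. Its objective is worded as estimation, and Protocol 10.6.3 says conclusions will focus on the estimate and the plausible values of the GMR. Interval width is therefore much of what this comparison delivers. With 15 women in one group, an avoidable share of residual variance is worth removing.

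Leaving adjustment optional, with the covariate open, also means that in an open-label study both choices could be made after the results are known.

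**Working it through.** **Inputs from the documents.** n = 15 (A) and 30 (B), two-sided 5% level, ratio 1.475 (Protocol 10.4). CV 0.45, giving a log-scale SD of 0.429 (SAP 2.3). At most 3 obese women in A and 5 in B (Protocol 10.3). AUC 49% lower (0–2.5 h, BMI above 35 vs below 25) and 52% lower (0–24 h, BMI above 30 vs below 25) (Protocol 2.1.1).

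**Step 1: reproduce the plan's figure.**
- SD = √ln(1 + 0.45²) = √0.1844 = 0.4294.
- SE = 0.4294 × √(1/15 + 1/30) = 0.1358.
- With t(43 df) = 2.0167, the half-width is 0.2739, a factor of exp(0.2739) = 1.315.
- 1.475 ÷ 1.315 = 1.12 and 1.475 × 1.315 = 1.94, which matches the stated (112, 194).
- Noncentral t with ln(1.475)/0.1358 = 2.86 gives 79.9% power, against the stated 80%. The design figures therefore describe an unadjusted comparison.
- On a 90% interval (t = 1.681) the same calculation gives 88%.

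**Step 2: a range for R².** This is not in the documents, so it is an assumption.
- Obesity at the cap is 8/50 = 0.16. The variance explained is 0.16 × 0.84 × (ln 0.51)² = 0.0609 for a 49% reduction, and 0.16 × 0.84 × (ln 0.48)² = 0.0724 for 52%. Divided by 0.1844, these give R² of 0.33 and 0.39.
- One obese woman among 45 (p = 0.022), with a 49% reduction, gives R² of about 0.05.
- A continuous slope from the 52% contrast, assuming mean BMIs 12 to 16 units apart and a BMI SD of 2.5 to 3.6, gives R² of 0.07 to 0.26. Example: (0.734/12 × 3.6)² / 0.1844 = 0.26.

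I take 0.05 to 0.40.

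**Step 3: adjusted interval.** With one covariate, SE = 0.1358 × √(1 − R²) × √(1 + 1/41), with 42 df (t = 2.0181). The factor 1/41 is the expected cost of estimating the slope. At R² = 0.20, SE = 0.1358 × 0.894 × 1.012 = 0.1229 and the half-width is 0.248. The width ratio is 0.248/0.274 = 0.906.

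| R² | 95% CI at ratio 1.475 | Log-scale width | Power, 95% CI | Power, 90% CI |
|---|---|---|---|---|
| unadjusted | 1.12–1.94 | – | 80% | 88% |
| 0.05 | 1.13–1.93 | −1% | 81% | 89% |
| 0.10 | 1.13–1.92 | −4% | 83% | 90% |
| 0.20 | 1.15–1.89 | −9% | 87% | 93% |
| 0.30 | 1.17–1.86 | −15% | 91% | 95% |
| 0.40 | 1.19–1.83 | −22% | 95% | 97% |

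**Step 4: break-even.** (1 − R²) × (42/41) × (2.0181/2.0167)² = 1 gives R² of about 2.5%. Below that, adjustment slightly widens the interval.

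**Step 5: where it matters less or more.** If exposure doubles with dose (ratio 2, an assumption), unadjusted power on the 95% interval is 99.9% at CV 0.45, 92% at CV 0.70 and 79% at CV 0.90. At CV 0.70 and ratio 1.475, power goes from 48% to 51% at R² 0.10 and to 56% at R² 0.20. If CV 0.45 describes variability apart from obesity, a simulation with 7 obese women of 45 and a 49% reduction gives about 67% unadjusted and 79% adjusted.

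**The case against.** **Validity.** The unadjusted difference is unbiased under randomisation, matches the sizing and is uniform across the four contrasts. That stands: nothing here is wrong or contradictory, and what may be lost is efficiency.

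**Objective 5 already adjusts.** SAP 4.2.2 fits log PK parameters on body size with LNG dose and perpetrator drug, plus region and age where possible. All of Group C received 1.5 mg and all of Group D 3.0 mg. With both terms categorical, the dose coefficient is therefore identified only by A vs B, so a body-size-adjusted B/A ratio would be available. This stands in part: that ratio is not designated for Objective 1, and the model's stated purpose is the body-size association.

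**The SAP's test is a Wilcoxon.** Adjusting the GMR alone leaves the stated test unchanged, and on the SAP's 90% interval unadjusted power is 88%, not 80%. This stands, and the fix must deal with it.

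**The ratio of 1.475 is a detectable difference, not the expected effect.** Near a ratio of 2 at CV 0.45 the conclusion would rarely change. This also stands.

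**R² is assumed.** The cited contrasts use other AUC windows and well-separated BMI groups, and the caps shrink the variance available. At CV 0.70 with a BMI SD of 2.5, R² is only 0.03 to 0.06, close to break-even. The gain can be stated only as a range.

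**Two readings to avoid.** A reader might infer that B vs A is uniquely the smallest comparison, but A vs C is also 15 vs 30. A reader might also infer that BMI may be adjusted for only in CDC categories. SAP 4.1.2 lists those categories for examining imbalance, and SAP 4.2.2 fixes no covariate form.

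**Conclusion.** The point holds as one of lost precision in a secondary estimate. The designated B/A GMR uses no covariate, and adjustment of that pair is optional and unspecified, although the protocol names a prognostic factor that is measured on every woman.

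At CV 0.45, with R² assumed between 0.05 and 0.40, the log-scale interval would be about 1% to 22% narrower. Power at ratio 1.475 would rise from 80% to 81–95% on the protocol's 95% interval, and from 88% to 89–97% on the SAP's 90% interval.

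A reader might go further and infer that the comparison is biased or inadequately powered. The documents do not support that: randomisation protects the unadjusted estimate, the protocol's power figure reproduces, and at a ratio near 2 and the design CV power is already 99.9%. The point does not concern confounding in B vs C or D vs C.

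**What to change.** In SAP 4.2.2, state that the reported B/A GMR and CI for AUC0-8h come from a normal linear model on log AUC with group and one named continuous body-size covariate (log weight, or BMI in kg/m²). Keep the unadjusted GMR of SAP 4.2.1 as supporting.

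In the SAP 3.1 table, state that inference for Secondary Objective 1 rests on this adjusted interval, with the exact Wilcoxon test kept as an unadjusted supporting test. Otherwise the gain does not reach the stated test. State the confidence level there too, because Protocol 10.4 uses 95% for this contrast and the SAP table uses 90%.

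Settle the covariate before AUC is seen by group. If it has already been seen, label the adjusted result as post hoc.

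Cost: a few sentences, one model and one degree of freedom, with no new data. One covariate fits the SAP's own limit of one at a time. The downsides are a GMR conditional on body size, and a very slightly wider interval if R² is below about 2.5%.

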### 3.0 STUDY DESIGN

A5375 is a Phase II, open-label, four parallel group, partially randomized, PK study to assess if a double dose of LNG EC overcomes known DDI with EFV-based ART and RIF-containing TB therapy. The safety of double-dose LNG EC versus standard-dose will also be compared.

Participants will be volunteers who do not currently require EC for contraception. This study will enroll a total of 116 women who are 16 years of age or older. Group assignment will be determined by infection status (HIV or TB; participants cannot be coinfectd), and, for those who are living with HIV, by ART regimen at enrollment. Women living with HIV who are taking EFV-based ART will be randomized to Group A (17 participants) or B (33 participants) in a 1:2 ratio. Women taking DTG-based ART will be assigned to Group C (33 participants). Women who are HIV-negative and in the continuation phase of active TB treatment taking RIF and INH will be assigned to Group D (33 participants).

At study entry, participants in Groups A and C will receive a standard (1.5 mg) single dose of LNG EC. Participants in Groups B and D will receive a double (3.0 mg) dose of LNG EC. Intensive PK monitoring will be conducted pre-dose, and after the LNG EC dose. Women are expected to be at the clinical site while the initial 8 hour PK samples are collected and may return for the 24 and 48 hour samples.

Information about demographic factors that can affect drug concentrations such as age, ethnicity, disease state, and concomitant drug use will be collected on all participants. Whole blood will be collected and stored for pharmacogenetic analyses.

Body fat content will be estimated using weight, height, neck, hip, and waist measurements. Because LNG exposure is known to be inversely correlated with weight/BMI (i.e., women with an obese BMI have lower LNG exposure) [30, 31], women with a BMI  $\geq 30$  kg/m^2 will be limited to no more than five within each of Groups B-D, and no more than three within Group A. Therefore, the representation of obese women will be no more than 15% of the study sample, and stratification limits by group will help control for imbalance across groups for this potential confounder.

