2.2.2 Secondary Objectives

- 1) *To estimate the difference in LNG pharmacokinetic (PK) exposure with double-dose LNG EC compared to standard-dose LNG EC in women receiving EFV-based ART.*
- 2) *To estimate the difference in LNG PK exposure with standard-dose LNG EC in women receiving EFV-based ART compared to women receiving DTG-based ART.*

- 3) *To verify the absence of significant DDI between LNG EC and DTG-based ART.*
- 4) *To compare the safety of double-dose LNG EC compared to standard-dose LNG EC.*
- 5) *To evaluate the relationship between baseline measures of body weight (body fat percentage, total weight, and body mass index [BMI]) and LNG PK exposure.*

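### Secondary Objective 3 is estimated only in separate normal-BMI and obese subgroups; with at most five obese women in Group C the obese result will rarely be decisive, and a BMI-stratified overall ratio should be added

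*SAP*

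**What the plan says.** The third secondary objective is "To verify the absence of significant DDI between LNG EC and DTG-based ART" (SAP 2.2.2; the same in Protocol 1.3). Protocol 10.6 gives no separate analysis for it. SAP 4.2.2 does. The outcome is LNG AUC0-24h and the comparator is the LNG arms of a published study in women with normal and obese BMI. The estimates are described as "Within subgroups defined by normal BMI and obese BMI, the GMR and associated 90% CI", which "will be estimated between A5375 Group C (DTG) and this external historical control group". The SAP adds: "This analysis will use Satterthwaite calculation of standard error".

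That paragraph gives no combined or BMI-adjusted ratio, no lead subgroup, no subgroup cut-offs and no decision rule. SAP 3.2.2 extends the primary reference interval, (0.70, 1.43), to the additional LNG PK parameters, so it is the natural yardstick here, but SAP 4.2.2 does not say so for this objective. The adjusted ratios listed as a supplementary analysis in SAP 4.2.2 concern study-group comparisons, and the pairs listed in SAP 4.1.2 do not include the external one.

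Protocol 3.0 fixes the size of the obese stratum. Women with BMI of 30 or more are "limited to no more than five within each of Groups B-D, and no more than three within Group A". Group C has 33 women in all.

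**The concern.** The objective asks for evidence of no effect, which needs a narrow interval. Splitting Group C puts at most five women in one of the two comparisons, and the plan never combines what the strata say. A reader is left with one ratio of moderate precision and one of very low precision, and no statement of which answers the question. The risk is that an obese-subgroup interval that merely covers 1 is taken as support for no interaction. With 10 external obese women (assumed), CV 0.45 and a true 30% reduction, that interval would still cover 1 about 60% of the time.

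**Working it through.** **Inputs.** The no-effect bounds are (0.70, 1.43), judged by a 90% CI (SAP 2.3, 3.1, 3.2.2). The log-scale SD is sqrt(ln(CV²+1)) (SAP 2.3). For AUC over 24 hours, Protocol 10.4 quotes CVs from 0.45 to 0.90, with 0.70 from the package insert; it argues for the low end only because the primary outcome is AUC0-8h. The SDs are 0.429, 0.631 and 0.770 at CV 0.45, 0.70 and 0.90. Obese Group C has n = 5 at most. *Not in the documents, so assumed:* the external group sizes and the number of normal-BMI women in Group C. The true ratio is 1 throughout unless stated.

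**The plan's own figure first.** For 30 per group and CV 0.45, two one-sided t tests give 87.6% power (stated: 88%). The expected CI is exp(±1.672 × 0.429 × sqrt(2/30)) = (0.83, 1.20), as stated.

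**Obese stratum, unlimited external group.** The expected 90% CI is exp(±t(0.95, 4) × SD/√5), with t = 2.132:
- CV 0.45: exp(±2.132 × 0.429/2.236) = (0.66, 1.51)
- CV 0.70: (0.55, 1.83)
- CV 0.90: (0.48, 2.08)

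These are intervals at the expected SD. A sample of five can show a smaller SD, so the chance of lying inside the bounds is small but not zero (simulation, Satterthwaite CI):

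| External obese n (assumed) | CV 0.45 | CV 0.70 | CV 0.90 |
|---|---|---|---|
| 5 | 2% | 0.1% | <0.1% |
| 10 | 5% | 0.2% | <0.1% |
| 20 | 11% | 1.1% | 0.2% |
| 30 | 13% | 1.9% | 0.5% |
| unlimited | 16% | 3.5% | 1.4% |

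For comparison, Table 10.4-1 requires 26, 55 and 81 women per arm for 80% power at these bounds and CVs.

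**Normal-BMI stratum.** With 15 to 28 Group C women and 10 to 30 external women (assumed), the chance of meeting the bounds is 27% to 87% at CV 0.45 and 1% to 37% at CV 0.70.

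**Combining the strata.** Illustration: 16 normal-BMI and 5 obese Group C women, 10 external women per stratum. Fixed weights proportional to nm/(n+m) are 160/26 = 6.15 and 50/15 = 3.33, that is 0.65 and 0.35. With a common SD, the standard error is SD/√(6.15 + 3.33) = SD/3.08. With t(0.95, 37) = 1.687, the expected CI is exp(±1.687 × 0.429/3.08) = (0.79, 1.27) at CV 0.45 and (0.71, 1.41) at CV 0.70. For normal BMI alone it is (0.74, 1.35) and (0.64, 1.55). The simulated chance of lying within the bounds is:

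| CV | Normal BMI alone | Combined, estimated inverse-variance weights | Combined, fixed weights |
|---|---|---|---|
| 0.45 | 28% | 62% | 60% |
| 0.70 | 1% | 12% | 9% |
| 0.90 | 0.1% | <2% | 1% |

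At CV 0.70 the expected combined interval only just fits, so sampling variation usually pushes one limit outside.

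**Choice of weights.** Inverse-variance weights have to be estimated partly from five women. In simulation the nominal 90% interval then covers only about 86 to 87%. Fixed sample-size weights with a Satterthwaite interval cover 90%.

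**The case against.** Separate strata are defensible. Protocol 2.1.1 cites a 52% lower AUC0-24h at BMI above 30 than below 25, and the external study is organised by BMI, so a crude pooled ratio would be confounded by BMI mix. This stands, and it is why the remedy is a stratified ratio shown beside the two subgroup results. A combined ratio also assumes a common effect across strata, which five obese women cannot check. That stands as a real cost.

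Four stronger readings are tempting, and the documents do not support them:
- *The obese interval cannot fit the bounds.* It can: about 16% of the time at CV 0.45 with an unlimited external group.
- *The objective gets no answer.* The normal-BMI comparison has a useful chance of meeting the bounds at CV 0.45.
- *Women with BMI 25 to 30 are excluded.* This follows only if the cut-offs quoted in Protocol 2.1.1 are used. SAP 4.2.2 does not define the subgroups.
- *The validity of Group C as control depends on this check.* Protocol 2.1.4, 2.2 and SAP 3.1 base that role on DTG's metabolism and an expectation of no interaction. No primary analysis is conditional on Objective 3.

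Nor does the SAP make covering 1 the criterion for similarity. It judges similarity by bounds, and for safety it refuses to infer similarity from non-significance (SAP 3.2.1). The misreading is therefore a risk left open, not something the plan prescribes. The Analysis Implementation Plan, which is not among the documents, may add detail.

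**Conclusion.** The point holds as a minor improvement. The analysis of Objective 3 is split so that one half has at most five Group C women and little chance of showing no effect: 16%, 3.5% and 1.4% at CV 0.45, 0.70 and 0.90 even with unlimited external data. The information across both halves is never combined. The objective is weakened, not void.

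Combining helps most at CV 0.45. At the package-insert CV of 0.70 for AUC24, the combined interval would still miss the bounds in roughly nine of ten trials under the illustrated sizes. These results rest on the documents' CV range applying within BMI strata, on a true ratio of 1, and on the assumed numbers of external and normal-BMI women. Larger external groups would raise the chances.

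**What to change.** In SAP 4.2.2, under Secondary Objective 3:
- Add one BMI-stratified GMR for AUC0-24h, Group C versus the external control, as the lead estimate, compared with (0.70, 1.43). Combine the two within-stratum log-ratios with fixed weights nm/(n+m) and a Satterthwaite 90% CI. Avoid estimated inverse-variance weights.
- Keep both subgroup results and label the obese one descriptive.
- Define the BMI subgroups, and report how many Group C women fall in neither if cut-offs of below 25 and above 30 are used.
- State the common-ratio assumption, and state that at CV 0.70 the combined interval may well miss the bounds, so a miss would not by itself indicate an interaction.

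The cost is a few lines of SAP text and one calculation from the same external summary data. No new data are needed. The price is the common-ratio assumption, which this study cannot test.
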